## **5.13. Study Overview of Anti-SAP Treatment and $^{89}\text{Zr}$ -GSK2398852**

### **5.13.1. Unlabelled anti-SAP mAb Dose Selection**

The study aims to identify the dose range leading to “optimal”  $^{89}\text{Zr}$ -mAb radiotracer uptake in the heart.

It is anticipated that at very low doses of unlabelled anti-SAP mAb, the clearance of radio-labelled PK may be fast and the expected slow penetration from plasma to heart muscle interstitium may therefore lead to a low uptake of  $^{89}\text{Zr}$ -GSK2398852 in heart tissue. This may give a low radioactivity signal in the heart impairing the possibility to obtain a good measurement.

[figure not shown]
On the other hand, a low unlabelled anti-SAP mAb dose may be beneficial to the binding of  $^{89}\text{Zr}$ -GSK2398852 to amyloid-SAP complexes in the myocardium because of lack of competition with binding of radiolabelled compound from a possible excess of unlabelled mAb within the interstitial space.

At higher TMDs of anti-SAP mAb, the plasma clearance of  $^{89}\text{Zr}$ -GSK2398852 is expected to be slower, facilitating an increased uptake in the tissue interstitium, while at

the same time this may be associated with an increased risk of unlabelled anti-SAP mAb competing with binding of the radiolabelled mAb.

The search for “optimal dose” needs to consider an expected inter-subject variability in the read-out due to biological factors (Figure 4).

**Figure 4** Examples of inter- and intra-subject relationships between tissue / plasma SUV ratio across a range of unlabelled (“cold”) anti-SAP mAb mass doses

In order to increase the probability of obtaining data which provides a good cardiac signal we propose the following concept:

- The first subject in Part A, Dosing Session 1 is investigated with the TMD 80 mg (70 mg unlabelled anti-SAP mAb *plus* 10 mg Zr-GSK2398852). The 80 mg dose is selected because this is the lowest dose in which we have previous adequate human PK data, and these data indicate a terminal elimination half-life in the range of 15 hours. This relatively short plasma residence may hamper the cardiac uptake but is still predicted to have a potential for adequate cardiac signal.
  - The TMD for this subject’s Dosing Session 2 will be determined by the central study team based on data from Dosing Session 1. This will be communicated to the clinical site by filenote prior to Dosing Session 2.

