#### Local tissue radioactivity concentration in organs in Regions of Interest (RoI)

##### SUVpeak:

A small sphere of 10-12 mm diameter placed in a representative location as seen in the image or transferred from the CT scan. Average of voxel (picture element) values within this volume is calculated.

SUVmean:

A larger outline of the whole organ or representative area or volume as seen in the image or transferred from the CT scan. Average voxel values (picture elements) within this volume is calculated.

Total organ radioactivity amount in Regions of Interest (RoI)SUVtotal\_organ:

An outline of the whole volume of the organ attempting to capture the total amount of radioactivity in that organ, as defined in the PET images or transferred from CT scan. Average of voxel (picture element) values within this volume is calculated.

VOLUMEtotal\_organ:

Corresponding total volume of the organs above

The SUVtotal\_organ and VOLUMEtotal\_organ are used for calculation of fraction of administered dose in that organ.

The organs/tissues of interest for analysis include:

Local tissue radioactivity concentration in organs in Regions of Interest (RoI)

Where relevant and depending on radioactivity uptake pattern:

- A minimum of 5 anatomical positions within the heart (only in the specific heart scans)
- Up to 3 focal and 1 larger location in each of the lungs
- Up to 3 focal and 1 larger location in the liver
- One focal and one large area in spleen
- One focal and one large area in pancreas
- One cortex and one medulla focal area in each of the kidneys
- One large area in the brain
- One large area in one thigh muscle
- Up to 5 small areas of the skin

Other focal or larger areas may be included depending on features in the images

For the regions in the 4\*5 scans focused over the heart, separate and average values will be generated for each of the RoIs.

Total organ radioactivity amount in Regions of Interest (RoI)

- Heart
- Liver
- Spleen
- One lung
- Both kidneys

Other organs may be included depending on features in the images

The PiB studies, performed only across the heart will be evaluated regionally and as “polar maps” using an extracted parameter called “retention index” which indicates the degree of retention as compared to washout.

The WAT studies will be evaluated regionally with automatic software which generates values and “polar maps” representing absolute blood flow values.

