**10.3.7.1. Analysis of PET data**

The tissue SUV and plasma radio-PK values generated will constitute the primary information from the studies. Since plasma radio-PK will be dependent upon time after administration plus mass dose, it will be necessary to relate the tissue SUV to the instant and possibly also to the AUC of the plasma radio-PK.

It is expected that the tissue-to-plasma ratio of the mAb in the heart will be approximately 0.1-0.2 after equilibration between plasma and tissue interstitium. This is guided by an expected plasma space plus interstitium relative space of 0.1-0.2. Within the blood pool of the heart chambers the ratio is expected to be 0.5 (hematocrit about 0.5). We have placed a limit by which the tissue-to-plasma ratio in the cardiac muscle is indicative of entry to the interstitium and binding to amyloid-SAP complexes at 0.5 in balance between a sufficient increase as compared to passive distribution and avoidance of “spill-over” from cardiac blood pools.

More complex models of distribution between plasma and tissue will be explored.

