7. PRIMARY STATISTICAL ANALYSES

7.1. Primary Analyses

7.1.1. Endpoint / Variables

- Standardized Uptake Values (SUV) [i.e. Radioactivity concentrations] in focal anatomical locations within the heart, as well as SUV of the whole heart at different time points after ⁸⁹Zr-GSK2398852 administration and at different anti-SAP mAb TMDs.

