7.1.2. Summary Measure

Data will be listed according to the GSK reporting standards, where applicable. All PET imaging parameters will be listed. Individual subject plots for the PET imaging parameters will also be produced.

Note that, in any one subject in Part A, where the radiolabel PK and cardiac SUV profile of ⁸⁹Zr-GSK2398852 is consistent with myocardial uptake during either the 1st or 2nd dosing session (i.e. cardiac / plasma SUV ratio ≥ 0.5), the reproducibility of this specific unlabelled anti-SAP mAb dose in enabling myocardial uptake of ⁸⁹Zr-GSK2398852 may be evaluated by treating further subjects with the same unlabelled anti-SAP mAb mass dose.

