7.1.4. Statistical Analyses / Methods

Table 2 provides an overview of the planned primary analyses, with full details of data displays being presented in Appendix 9: List of Data Displays which will be based on GSK data standards and statistical principles.

Table 2 Overview of Planned Primary Analyses

Endpoint / Parameter / Display Type	Absolute			
	Summary		Individual	
	T	F	F	L
PET (cardiac images)				
For the whole heart: SUV _{mean} and volume For each cardiac focal anatomical location: SUV _{peak} over the entire 20-minute scan period, and volume			Y ¹	Y

NOTES :

[1] Figures will be restricted to SUV_{mean} values and SUV_{peak} values over the entire 20-minute scan period.

T = Table, F = Figure, L = Listing, Y = Yes display generated.

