12.9.12. Non-ICH Listings

Non-ICH: Listings					
No.	Population	IDSL / Example Shell	Title	Programming Notes	Deliverable [Priority]
Pharmacodynamic and Biomarkers					
33.	All Treated	PD_L1	Listing of Quantitative Derived Parameters of Cardiac PET Images of Focal Anatomical Locations		IA, SAC
34.	All Treated	PD_L2	Listing of Quantitative Derived Parameters of PET Images of Different Organs/ Tissues		IA, SAC
35.	Safety	PD_L3	Listing of Troponin T and NT-ProBNP		IA, SAC
36.	Safety	PK07	Listing Plasma SAP concentrations		IA, SAC
Safety					
37.	Safety	SAFE_L1	Listing of Cardiac Telemetry		IA, SAC
PK					
38.	PK	PK07	Listing of Plasma Concentration Time Data of 89Zr-GSK2398852		IA, SAC
39.	PK	PK07	Listing of Whole Blood Concentration Time Data of 89Zr-GSK2398852		IA, SAC
40.	PK	PK07	Listing of Plasma Concentration Time Data of Total mAb		IA, SAC
41.	PK	PK13	Listing of Derived Pharmacokinetic Parameters for Plasma Concentration of 89Zr-GSK2398852		IA, SAC
42.	PK	PK13	Listing of Derived Pharmacokinetic Parameters for Plasma Concentration of Total mAb		IA, SAC

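### Raw whole-heart SUV can rise with total mass dose without any binding, and, separately, the 0.5 tissue/plasma limit has no margin over chamber blood

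*Protocol*

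**What the plan says.** **Whole-heart measure.** The primary endpoint (Protocol 4, SAP 7.1.1) covers focal heart regions "as well as SUV of the whole heart at different time points" and at different TMDs. Protocol 10.3.7 defines SUVmean as the voxel average over "A larger outline of the whole organ or representative area or volume as seen in the image or transferred from the CT scan". It neither excludes the chambers nor describes a blood correction. In SAP 7.1.4, the Table 2 row that begins "For the whole heart: SUV" gives the mean and the volume, as a listing and an individual figure. In SAP Appendix 9 these are Listing 34 and Figure 2.2.

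**Clearance.** Protocol 5.13.1 gives a terminal half-life of about 15 h at TMD 80 mg. The sentence opening "At higher TMDs of anti-SAP mAb, the plasma clearance of" the labelled antibody says that clearance should be slower there, without a figure.

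**Limit.** Protocol 10.3.7.1, repeated in SAP 12.4.5, expects a passive heart ratio of 0.1 to 0.2 and explains: "This is guided by an expected plasma space plus interstitium relative space of 0.1-0.2". For the chambers it says: "Within the blood pool of the heart chambers the ratio is expected to be 0.5 (hematocrit about 0.5". It then sets the limit for cardiac muscle at 0.5, partly to avoid spill-over from the chambers. The decision text in Protocol 10.3.3 and 10.3.4 and in SAP 7.1.2 is looser: "i.e. cardiac / plasma SUV ratio ≥ 0.5", with no region named.

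**Related plans and data.** Protocol 10.3.7.1 accepts that tissue SUV must be related to plasma radioactivity. SAP 9.1.3 describes a model for each heart region with a vascular component. Haematocrit is in the haematology panel (Protocol Appendix 2), and whole blood is sampled (Protocol 3.3.1). SAP 12.9.12 includes a "Listing of Whole Blood Concentration Time Data of 89Zr-GSK2398852", and the shell for Listing 33 shows LA, LV and RV blood regions beside wall and septum.

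**The concern.** There are two faults, and they do not depend on each other.

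First, chamber blood and unbound interstitial tracer both follow plasma. If plasma clears more slowly at a higher TMD, a raw whole-heart value goes up at the same scan time whether or not more antibody has bound. The comparison across TMDs is the primary objective. Protocol 10.3.4 also looks for the opposite change: a fall in cardiac signal at a higher dose, read as displacement. Slower clearance could hide that fall.

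Second, a limit meant to tell muscle uptake from blood pool is set at the value that the protocol itself expects for blood. Because the rule is at or above 0.5, pure blood meets it, and it does so with room to spare at any haematocrit below 0.5.

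**Working it through.** **Inputs from the documents:** blood/plasma 0.5 at haematocrit (Hct) about 0.5; passive muscle ratio p = 0.1 to 0.2; limit 0.5; half-life 15 h at TMD 80 mg; first subject's scans at 5, 24 and 72 h.

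**Assumed:** half-life T at a higher TMD of 20 to 48 h with the same distribution volume; chamber share c of the outline of 0.3 to 0.7; Hct of 0.35 to 0.45 as the alternative to 0.5.

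**1. The plan's figure.** For tracer confined to plasma, blood/plasma = 1 − Hct = 1 − 0.5 = 0.5. This reproduces.

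**2. Clearance and raw SUV.** Relative to a 15 h half-life, plasma and blood activity at time t change by the factor 2^(t/15 − t/T). With no binding and tissue in equilibrium with plasma, so does whole-heart SUV.

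| T (h) | 5 h | 24 h | 72 h |
|---|---|---|---|
| 20 | 1.06 | 1.32 | 2.30 |
| 24 | 1.09 | 1.52 | 3.48 |
| 30 | 1.12 | 1.74 | 5.28 |
| 48 | 1.17 | 2.14 | 9.85 |

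For T = 24 h: 2^(1.6 − 1.0) = 1.52 at 24 h and 2^(4.8 − 3.0) = 3.48 at 72 h. The 72 h levels are low in absolute terms: 3.6% of the starting activity at 15 h and 12.5% at 24 h.

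**3. How much of the passive signal is blood.** With blood 0.5 and tissue 0.2, the share is 0.5c/(0.5c + 0.2(1 − c)). At c = 0.3 this is 0.15/0.29 = 52%. At c = 0.6 it is 0.30/0.38 = 79%.

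**4. Displacement, illustrated.** Take c = 0.5, Hct 0.5, p = 0.2, and a session 1 muscle ratio of exactly 0.5 at the scan in question.
- Session 1 whole heart: 0.5×0.5 + 0.5×0.5 = 0.50 times plasma.
- Session 2 with all binding displaced: 0.5×0.5 + 0.5×0.2 = 0.35 times plasma.
- With T = 24 h in session 2, in units of session 1 plasma: 0.35×1.52 = 0.53 at 24 h and 0.35×3.48 = 1.22 at 72 h, against 0.50.

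Raw whole-heart SUV would be flat or higher although displacement was complete. The ratio to plasma would fall from 0.50 to 0.35.

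**5. Limit against blood.** 1 − Hct gives 0.55, 0.60 and 0.65 at Hct 0.45, 0.40 and 0.35. The blood fraction that a wall region without binding needs to reach 0.5 is (0.5 − p)/((1 − Hct) − p). At p = 0.2 this is 0.30/0.35 = 86%, 0.30/0.40 = 75% and 0.30/0.45 = 67%. At Hct 0.5 it is 100%.

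**6. Whole-heart ratio without binding:** c(1 − Hct) + (1 − c)p, which contains no TMD term. At c = 0.5, Hct 0.40, p = 0.2 it is 0.30 + 0.10 = 0.40. Over c 0.3 to 0.7, Hct 0.35 to 0.50 and p 0.1 to 0.2 it runs from 0.3×0.50 + 0.7×0.1 = 0.22 to 0.7×0.65 + 0.3×0.2 = 0.52. In steps of 0.1 in c and 0.05 in Hct, only that last corner reaches 0.5. The outline still lowers the bar: at c = 0.5 and Hct 0.40 it reads 0.5 when muscle is at (0.5 − 0.30)/0.5 = 0.40.

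**7. Tissue lag.** If interstitium equilibrates with an assumed half-time of 12 h, with a = ln2/12 and k = ln2/T, the passive ratio is p·a/(a − k)·(1 − exp(−(a − k)t)). At p = 0.2 and 72 h this is 0.57 for T = 15 h and 0.31 for T = 30 h.

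**The case against.** The sponsor has seen the blood-pool problem. Protocol 10.3.7.1 says plasma radioactivity depends on time and mass dose and that tissue must be related to it. Protocol 5.13.2 justifies the late scan because earlier ones are more likely to show chamber blood. SAP 3.1 pairs cardiac SUV with plasma radio-PK for the in-stream review. So a reader who infers that the blood data are collected and ignored goes too far. What remains is delivery. SAP Appendix 9 has no heart/plasma or heart/blood ratio and no identifiable model output. Table 4.5 is arranged by heart region but is titled as plasma concentration data.

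A reader might also infer that the assumed haematocrit makes a higher TMD look better. It does not. The limit is a ratio to plasma, and 1 − Hct does not depend on TMD (step 6). If tissue lags plasma, the ratio is biased towards the lower TMD (step 7).

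Nor does the limit fail for ordinary wall regions: at p = 0.2 they need mostly blood to pass. Protocol 3.3.3 says extracellular volume is raised in amyloid hearts but gives no value, so a higher passive ratio would be an assumption. The limit also opens only optional evaluations, alongside the PK profile.

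Finally, inclusion of the chambers is inferred from the SUVmean definition. The Imaging Acquisition and Analysis Manual, which is not among the documents, may define the heart outline more tightly. Excluding chamber blood would not by itself cure the first fault, because passive interstitial tracer also follows plasma.

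**Conclusion.** Both faults hold, separately.

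- **Raw whole-heart SUV** can increase with TMD without binding. The size depends on how far clearance slows, which the documents do not say. For a half-life of 24 h instead of 15 h the factor is about 1.1 at 5 h, 1.5 at 24 h and 3.5 at 72 h. The same shift could mask the attenuation sought in Protocol 10.3.4.
- **The 0.5 limit** equals the expected blood ratio at haematocrit 0.5 and lies below it at any lower value, so it does not separate muscle from blood as Protocol 10.3.7.1 intends. The practical risk is small for clean wall regions and largest for the whole-heart outline or heavily contaminated regions. The decision text does not rule those out.

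The study is exploratory, with no hypothesis test, and PET results are listings and individual plots for up to six subjects. The consequence is a misread profile or dose comparison rather than a wrong test result. With so few profiles and no PET summary statistics (SAP 2.2), such an artefact would not average out. The change is worth making before the displays are final.

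**What to change.** 1. Add to SAP Appendix 9 a listing and individual plots, by subject, session and TMD and at each scan time, of wall, septal and whole-heart SUV divided by (a) time-matched plasma and (b) blood, from the LV-blood region of the same scan or measured whole-blood activity. Put plasma and whole-blood activity on the SUV scale first, and state how values are interpolated to the scan time.
2. State that raw whole-heart SUV is compared across TMDs only alongside these ratios. Read late ratios at low TMD with the lag in step 7 in mind.
3. Replace the assumed blood ratio of 0.5 with each subject's measured whole-blood/plasma ratio, or 1 minus haematocrit. Require the muscle/plasma ratio to exceed it as well as meeting 0.5.
4. In Protocol 10.3.3 and 10.3.4 and SAP 7.1.2, say, as Protocol 10.3.7.1 does, that the rule applies to wall and septal muscle regions and not to the whole-heart outline.
5. List the output of the model described in SAP 9.1.3, or say that it will be reported elsewhere.

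**Cost.** Items 1 to 4 are text and a few derived columns from Listings 33, 34, 38 and 39 plus haematocrit, with no added procedure for subjects. The limit becomes somewhat stricter: at haematocrit 0.40 it moves from 0.50 to 0.60. Subtracting chamber blood from the whole-heart value should stay optional, since it needs the blood fraction of the outline, and hence chamber segmentation that no listing provides.

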**10.3.7.2. Storage and potential further analyses of images**

The primary PET and CT images in digital form will be anonymized and stored in an image repository under the control of GSK and may be used for further analyses

**10.3.8. Safety**

The All Treated Population will be used for the analysis of safety data. All serially collected safety endpoints (e.g. laboratory tests, vital signs, ECGs) will be summarised according to the scheduled, nominal visit at which they were collected and across all on-treatment time points using a “worst-case” analysis. Complete details of the safety analyses will be provided in the RAP.

## 12. APPENDICES

### 12.1. Appendix 1 Abbreviations and Trademarks

#### Abbreviations

 Zr-GSK2398852	 Zirconium-labelled anti-SAP mAb
99m Tc-DPD	Technetium-99m-labelled 3,3-diphosphono-1,2-propanodicarboxylic acid
AE	Adverse Event
AL	Amyloid Light-chain
ALARP	As Low as Reasonably Practicable
ALT	Alanine transaminase
anti-SAP	anti-Serum Amyloid P component
aPTT	activated partial thromboplastin time
AST	Aspartate transaminase
ATTR-CM	Transthyretin amyloidosis restrictive cardiomyopathy
AUC	Area Under the Curve
Bq	Becquerel
BSA	Body surface area
BUN	Blood urea nitrogen
CABG	Coronary Artery Bypass Grafting
CIOMS	Council for International Organizations of Medical Sciences
cm	Centimetre
C max	Maximum Concentration
CMR	Cardiac Magnetic Resonance Imaging
CPK	Creatine phosphokinase
Cold anti-SAP mAb	Unlabelled anti-SAP mAb
CONSORT	Consolidated Standards of Reporting Trials
CPHPC	GSK2315698 (Carboxy pyrrolidine hexanoyl pyrrolidine carboxylate)
CRF	Case report form
CRNA	Complementary ribonucleic acid
CSR	Clinical Study Report
CT	Computerised Tomography
CV	Cardiovascular
Df	desferrioxamine

ECG	Electrocardiogram (12-lead)
ECHO	Echocardiogram
ECV	Cardiac Extracellular Volume
eGFR	Estimated Glomerular Filtration Rate
FAC	Familial Amyloidotic Cardiomyopathy
FcRn	neonatal Fc receptor
FDA	Food and Drug administration
FDG	Fludeoxyglucose
FIH	First in Human
FSH	Follicle stimulating hormone
GBM	Glomerulus basement membrane
GCP	Good Clinical Practice
Gd	Gadolinium
GSK	GlaxoSmithKline
GSK2315698	CPHPC (Carboxy pyrrolidine hexanoyl pyrrolidine carboxylate).
GSK2398852	Unlabelled anti-SAP mAb
h	hour
HBsAg	Hepatitis B surface antigen
HCG	Human chorionic gonadotropin
HFpEF	Heart failure with preserved ejection fraction
HIPAA	Health Insurance Portability and Accountability Act
HIV	Human Immunodeficiency Virus
HPLC	High performance liquid chromatography
HRT	Hormonal replacement therapy
hs-cTn	High Sensitivity Cardiac Troponin
IB	Investigator's Brochure

ICD	Implantable Cardiac Defibrillator
ICF	Informed Consent Form
IEC	Independent ethics committee
IgA	Immunoglobulin A
IgG	Immunoglobulin G
IMP	Investigational Medical Product
INR	International normalized ratio
IP	Investigational Product
IRB	Institutional Review Board
IRR	Infusion Related Reaction
IUD	Intrauterine device
IUS	Intrauterine hormone-releasing system
IV	Intravenous
L	Litre
LCV	Leukocytoclastic vasculitis
LDH	Lactate dehydrogenase
LV	Left ventricle
LVAD	Left Ventricular Assist Device
mAb	Monoclonal antibody
MBq	Megabecquerel
MCH	Mean corpuscular hemoglobin
MDRD	Modification of Diet in Renal Disease
MedDRA	Medical Dictionary for Regulatory Activities
mg	Milligram
Mg/dL	Milligram per decilitre
MGC	Multinucleate giant cells
µmol/L	Micromol/litre
mL	Millilitre
mm	Millimetre
mmHg	Millimetre of mercury
MRI	Magnetic Resonance Imaging
MSDS	Material Safety Data Sheet
msec	Millisecond
mSv	Millisievert
NSD	Nephrogenic systemic dermatopathy
NSF	Nephrogenic systemic fibrosis
NT-proBNP	N-terminal prohormone of brain natriuretic peptide

NYHA	New York Heart Association
O	Oxygen
PD	Pharmacodynamics
PET	Positron Emission Tomography
PET/CT	Positron Emission Tomography and Computed Tomography (combined scan)
PI	Principal Investigator
PiB	Pittsburgh Compound B (binds to amyloid deposit)
PIH	Post-Inflammatory Hyperpigmentation
PK	Pharmacokinetic
PPM	Permanent Pacemaker
PT	Prothrombin time
QTcF	Interval from the Q wave on the ECG to point T using Fredericia's formula
QTcB	QTc corrected by Bazett's formula
RAP	Reporting and Analysis Plan
RoI	Regions of Interest
SAE	Serious Adverse Event
SAP	Serum Amyloid P Component
SC	Subcutaneous
SCr	Serum Creatinine
SD	Starting dose
SGOT	Serum Glutamic-Oxaloacetic Transaminase
SGPT	Serum Glutamic-Pyruvic Transaminase
Sec	Seconds
siRNA	Small interfering ribonucleic acid
SoA	Schedule of Activities
SOP	Standard Operating Procedure
SPECT imaging	Single-photon emission computed tomography
SRM	Study Reference Manual
SUSAR	Suspected Unexpected Serious Adverse Reactions

SUV	Standardized Uptake Values (Measured radioactivity concentration corrected for radioactive decay and normalized for administered amount of radioactivity per body weight)
T 1/2	Half-life
Tc-DPD	Technetium-99m-labelled 3,3-diphosphono-1,2-propanodicarboxylic acid
TID	Thrice daily
T max	Time to reach maximum concentration
TMD	Total Mass Dose
TNF	Tumor necrosis factor
TTR	Transthyretin amyloidosis

TTS	Study Specific Technical Agreement/Memo
TUDCA	Tauroursodeoxycholic acid
ULN	Upper Limit of Normal
Unlabelled anti-SAP mAb	GSK2398852
US	United States
VF	Ventricular Fibrillation
VT	Ventricular Tachycardia
WAT	15-Oxygen labelled water
WBC	White blood cell
WOCBP	Woman of Childbearing Potential
w/v	Weight by volume
Zr	Zirconium

